## 1. Introduction

This document details the planned analyses for Study 191622-137, a multicenter, randomized, double-blind, parallel group, multi dose study to evaluate the safety and efficacy of BOTOX for the treatment of urinary incontinence due to overactive bladder (OAB) in patients 12 to 17 years of age who have not been adequately managed with anticholinergic therapy.

There will only be one analysis for this study. When all patients in Study 191622-137 exit the study, there will be a database lock (DBL), and a clinical study report (CSR) will be generated. This analysis plan outlines the outputs to be included in the CSR.

### 1.1 Primary Study Objectives and Design

The primary objective is to evaluate the safety and efficacy for the treatment of urinary incontinence due to OAB in patients 12 to 17 years of age who have not been adequately managed with anticholinergic therapy.

Patients may participate in the study for 96 weeks following entry into the study and should have at least 12 weeks follow-up since the last treatment prior to exiting the study. Eligible patients are randomized to 1 of 3 treatment groups in a 1:1:1 ratio:

- 25 units (U) BOTOX (not to exceed 6 U/kg)
- 50 U BOTOX (not to exceed 6 U/kg)
- 100 U BOTOX (not to exceed 6 U/kg)

In order to ensure that an upper dosing limit of 6 U/kg is not exceeded, the actual dose administered will be adjusted based on the patient's weight if necessary.

Patients will be centrally randomized. In order to ensure balance across treatment groups, patients will be stratified by baseline daytime urinary urgency incontinence episodes (a total of  $\leq 6$  episodes or  $> 6$  episodes over the 2-day diary collection period).

Multiple treatments may be administered in this study. Doses received at subsequent retreatments will be determined by the investigator and based on the patient's response to the preceding blinded treatment. The investigator can elect to keep the dose the same or increase the dose compared with the preceding treatment. If it is deemed that a decrease in dose is warranted, the patient will be exited from the study. The first treatment will be administered on day 1.

All patients will be evaluated at scheduled clinic visits at weeks 2, 6, and 12 post-treatment, and thereafter at alternating telephone and clinic visits every 6 weeks until the patient qualifies for further retreatment or exits the study. Patients can request retreatment from week 12 since the preceding treatment. Once qualified for retreatment, the same visit schedule will be followed.

The primary efficacy measure is daytime urinary incontinence episodes, and the primary time point is week 12 after treatment 1.

## 1.2 Secondary and Other Objectives

This section is not applicable.

## 1.3 Sample Size

The sample size calculation for this study is determined empirically. A total of approximately 108 patients are to be enrolled for the study (32 per treatment group plus 10% attrition).

The following table displays the estimated differences between 100 U of BOTOX (maximum 6 U/kg) and 25 U of BOTOX (maximum 6 U/kg) in mean daily average frequency of daytime episodes of urinary incontinence change from baseline at week 12 for a range of common standard deviations (SDs). All calculations assume 32 patients per treatment group and a 2-sided test significance level of 0.05. The calculation was performed using the commercial software nQuery Advisor (procedure MTC0-1), version 6.01 (Statistical Solutions Ltd., Cork, Ireland), and the CI for the difference of 2 means based on normal distribution.

Standard Deviation	Distance From Mean to the Limit
2.0	0.980
2.5	1.225
3.0	1.470
3.5	1.715
4.0	1.960

Note: The ranges of the SDs are determined based on the values from Allergan's 2 pivotal phase 3 OAB studies, 191622-095 and 191622-520. The estimate of the SD for the 100-U BOTOX treatment group is 3.33 for Study 191622-095, 3.58 for Study 191622-520, and 3.46 for the 2 studies combined. The distance from mean to limit indicates how much the CI for the mean extends from the observed difference in means in either direction.

## 1.4 Experimental Unit and Analysis Unit

The experimental unit is study subject. The primary efficacy assessment is daytime urinary incontinence episodes measured at the patient level.

## 2. Analysis Populations and Data Conventions

### 2.1 Analysis Populations

Patients may receive multiple treatments in this study. Eligible patients are initially randomized to one of three treatment groups, namely, 25, 50, or 100 U BOTOX treatment groups. The investigator can elect to administer subsequent retreatments in a blinded fashion by keeping the dose the same or increase the dose compared with the preceding treatment. The dose that is actually received by a patient can vary due to the dose limit of 6 U/kg (i.e., the dose is adjusted based on the patient's weight, see Section 12.1 of the study protocol for details).

In order to maintain blinding of the BOTOX dose received, the drug is reconstituted by an independent drug reconstitutor (IDR) based on treatment assigned by IVRS/IWRS (which also includes the patient's weight as provided in IVRS/IWRS). Study drug accountability and reconstitution records are then reviewed and confirmed by independent drug monitors (IDM). If an incorrect dose was administered, the IDM will complete the "Incorrect Unit Dose Administered" form and the "incorrect unit dose administered" will be entered into the electronic case report form (eCRF).

The actual dose unit received by a patient will be derived as follows:

1. If the "incorrect unit dose administered" is populated in the eCRF, this dose will represent the actual dose unit received.
2. If the "incorrect unit dose administered" is not populated in the eCRF, then the IVRS/IWRS assigned dose (ie, 25U, 50U, or 100U) and the patient's weight recorded in IVRS/IWRS at the treatment visit will be utilized to determine the actual dose unit administered as described in Section 12.1 of the study protocol.

One analysis population will be used in the statistical analysis of this study: the BOTOX-Treated Population. The BOTOX-Treated Population will include all patients enrolled into the study who received at least 1 BOTOX treatment and will be used for all efficacy and safety analyses. The BOTOX treatment group used for analysis in each treatment cycle will be derived as stated in [Table 1](#) below based on the dose actually received in the respective treatment cycle.

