5.3 Methods for Blinding

Both patients and investigators will remain blinded to BOTOX dosage (unless the patient is requested to exit the study via the IVRS/IWRS due to dosing request, as described at the end of Section 5.5).

The study medication will be packaged and labeled in identically appearing vials and reconstituted to the same volume by an independent drug reconstitutor (IDR) who is not associated or involved with a study patient's care or study assessments, with the exception of study medication preparation. The study medication will be identified as an investigational compound and the carton will also be labeled with the study number and kit number.

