7.1 Analysis Populations

Two analysis populations will be used in the statistical analysis of this study: the BOTOX-treated population and the BOTOX-treated per protocol (PP) population.

The BOTOX-treated population will include all patients enrolled into the study who received at least 1 BOTOX treatment and will be used for all efficacy and safety analyses. Analyses will be based on the treatment actually received in each treatment cycle. Patients will be grouped to the nearest dose group (25 U, 50 U, or 100 U BOTOX) based on the dose actually received.

The BOTOX-treated PP population will include all randomized patients with no major protocol deviations on an as-treated basis (ie, using the dose actually received with all patients allocated to the nearest dose group [25 U, 50 U, or 100 U BOTOX]). More detailed criteria for the definition of this population will be given in the statistical analysis plan. The

list of patients excluded from the PP population will be finalized prior to the database lock. The primary efficacy variable will also be analyzed using the PP population in a sensitivity analysis.

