8.2 Procedures for Final Study Entry

Final study eligibility will be determined at the randomization/day 1 visit to confirm that patient bladder diary records support protocol requirements for urinary urgency incontinence. In addition, prior to randomization, the investigator should confirm that all “day of treatment

criteria” have been fulfilled (Section 5.9.1). Patients should continue to meet other inclusion and exclusion criteria as specified in Sections 4.3 and 4.4 of the protocol.

A patient is considered to have entered the study when they are randomized to treatment.

See Section 5.5 for the method for assignment to treatment groups/randomization.

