### 2.3.1 Diary Data Conventions

- For baseline and post-treatment visits, analyses will be based on the diary data collected over 2 consecutive days. For each day, the bladder diary will be used to collect wake time (time patients woke up to start the day), bedtime (time patients go to bed to sleep at night), urinary episodes (incontinence, urgency, catheterization, or voluntary void) during the daytime collection period, volume of each void over 1 daytime period, and presence/absence of nighttime urinary incontinence.
- A valid diary day is defined as a day where there are 1 or more urinary episodes of any type (incontinence, catheterization, or voluntary void) during the daytime collection period. In the case of patients who partially complete their diary, providing that at least 1 valid diary day out of 2 is available, the 2-day frequency of daytime urinary incontinence will be prorated with the value from the valid diary day, i.e. it is the average of the daytime urinary incontinence in the valid diary day multiplied by 2.
- If less than 1 diary day out of 2 has been completed, the frequency of daytime urinary incontinence will be set to missing.
- Missing daily average frequency of episodes of daytime urinary incontinence at baseline will be imputed using the median of all non-missing values at baseline within the same treatment dose group received for the first treatment (grouped to the nearest dose group based on the dose actually received). For scheduled visits up to week 12 after the first study treatment, missing daily average frequency of episodes of daytime urinary incontinence will be replaced using the last observation carried forward (LOCF) approach. Baseline values will not be carried forward. No imputation will be done for missing values on visits after the post-treatment 1 week 12 visit.

- For normalization of frequency of daytime urinary incontinence episodes in a given day to a 12-hour daytime period, the following algorithm will be used:
  - Apply visit window defined in Section 2.2 that uses days from treatment as reference.
  - Identify wake time and bedtime within the visit window. Daytime period (in hours) is determined by time between wake time and bedtime for that day.
  - Using the example below, 4 urinary incontinence episodes are recorded during the first daytime period of 16 hours (7:00am to 11:00pm), and 7 urinary incontinence episodes are recorded during the second daytime period of 14 hours (8:30am to 10:30pm).

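### Low severity: a recorded cycle 1 dosing error can move a patient to another arm in the week 12 tests, and no as-randomised efficacy analysis is planned

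*SAP*

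**What the plan says.** SAP 2.1 defines one population, the treated patients, for all efficacy and safety analyses. The analysis group in each cycle is set "based on the dose actually received in the respective treatment cycle", with cut-offs at 37.5 U and 75 U in Table 1. Protocol 7.1 has the same rule: "Analyses will be based on the treatment actually received in each treatment cycle".

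SAP 2.1 derives the received dose in two steps. If the eCRF holds an incorrect dose, "this dose will represent the actual dose unit received". Otherwise the dose follows from the IVRS/IWRS assignment and the recorded weight, using the preparation tables in Protocol 12.1.

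SAP 5.2.1 then tests 100 U against 25 U, and 50 U against 25 U if the first is significant, at week 12 of cycle 1. The MMRM in SAP 5.2.2 examines the LOCF imputation and does not change the grouping. The per-protocol set in Protocol 7.1 was also as-treated, and SAP 15 records its deletion. Baseline imputation in SAP 2.3.1 likewise works "within the same treatment dose group received for the first treatment".

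**The concern.** Dose is randomised in cycle 1, and the two confirmatory hypotheses compare the dose groups formed by that randomisation. A dosing error happens after randomisation. Under SAP 2.1 such an error, if large enough, decides which arm the patient counts in.

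Comparing patients as randomised is protected whatever caused the error. Grouping by dose received also needs errors to be unrelated to prognosis. The plan contains no analysis that would show a reader whether this mattered.

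The point is confined to cycle 1. From cycle 2 the investigator decides whether to keep or raise the dose, so there is no randomised grouping to preserve and dose received is the sensible choice.

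**Working it through.** **Inputs.** SAP 1.3: 32 per group, two-sided 0.05, SD 3.46 (combined adult studies). SAP Table 1: cut-offs 37.5 U and 75 U. Protocol 12.1: preparation volumes. Assumed, because the documents give no figure: one mis-dosed patient; a deviation of 0.5 to 1 SD from the arm mean; 16 per arm as a smaller-trial case. SAP 15 says recruitment was stopped but gives no final number, and SAP 1.3 still says about 108.

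**The plan's own figures.** Half-width = 1.96 × SD × √(2/32). SD 2.0, 2.5, 3.0, 3.5 and 4.0 give 0.980, 1.225, 1.470, 1.715 and 1.960, as tabulated. 32/0.9 rounds up to 36 per group, and 3 × 36 = 108. At SD 3.46 the half-width is 1.695 for 32 per arm and 2.398 for 16.

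**Can the weight cap move anyone?** A 100 U vial in 5 mL gives 20 U/mL. The volumes 1.25, 2.5, 4.2, 4.8 and 5.0 mL give 25, 50, 84, 96 and 100 U. The first stays in the 25 U group, the second in the 50 U group, and the last three in the 100 U group. At 6 U/kg, the 100 U arm would fall below 75 U only under 75/6 = 12.5 kg, and the 50 U arm below 37.5 U only under 37.5/6 = 6.25 kg. The preparation tables start at 14 kg. The cap moves nobody.

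**Errors unrelated to prognosis.** Moving such a patient only turns arm sizes n and n into n − 1 and n + 1. Under the null the test keeps its 5% level.

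**One moved patient who differs by d from the arm mean, under the null.** The shift in the difference is d/(n − 1) + d/(n + 1) = 2nd/(n² − 1). Type I error is approximately P(|Z + shift/SE| > 1.96), with SE = 3.46 × √(2/n).

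| n per arm | d | Shift (episodes/day) | SE | Share of half-width | Type I error |
|---|---|---|---|---|---|
| 32 | 1.73 (0.5 SD) | 64 × 1.73/1023 = 0.108 | 0.865 | 6% | 5.2% |
| 32 | 3.46 (1 SD) | 64 × 3.46/1023 = 0.216 | 0.865 | 13% | 5.7% |
| 16 (assumed) | 1.73 | 32 × 1.73/255 = 0.217 | 1.223 | 9% | 5.4% |
| 16 (assumed) | 3.46 | 32 × 3.46/255 = 0.434 | 1.223 | 18% | 6.5% |

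A simulation of the three-arm ANCOVA (20,000 runs per setting) with slightly smaller deviations gave slightly lower values: 5.1% and 5.5% at 32 per arm (0.48 and 0.93 SD), and 5.4% and 5.9% at 16 (0.46 and 0.87 SD).

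**Price of as-randomised grouping.** If one patient is mis-dosed between 100 U and 25 U, a true difference Δ is diluted by Δ/n. For an assumed Δ of 2 episodes/day:
- 32 per arm: 2 − 2/32 = 1.9375, and power falls from 63.8% to 61.0%.
- 16 per arm: 2 − 2/16 = 1.875, and power falls from 37.3% to 33.5%.

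By dose received, with arms of n − 1 and n + 1, power would be 63.7% and 37.2%.

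**The case against.** The strongest reply is that there is no defect to correct. The rule is prespecified, protocol and SAP agree on it, and cycle 1 grouping is as randomised unless an error is recorded. All of that stands.

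Safeguards also make a link between errors and prognosis unlikely. Someone outside the patient's care prepares the dose (Protocol 5.3), patients and investigators are blinded, and "reconstitution records are then reviewed and confirmed by independent drug monitors" (SAP 2.1). SAP 3.4 tabulates significant deviations, though the documents do not show whether a wrong dose counts as one. This limits the likely bias. It does not supply the missing comparison.

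A further reply is that replacing the protocol's primary grouping is more than the problem needs, and that a sensitivity analysis with a count would answer it. That has force, and it is offered below as the minimum. The power cost is also real, so the change is cheap but not free.

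A reader might infer more than the documents support:
- That the 6 U/kg cap reshuffles the arms. No planned dose crosses a cut-off.
- That the primary test is biased. The documents report no cycle 1 dosing error and no link between errors and prognosis.
- That the SAP departs from the protocol on this point. Both state the same rule.

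**Conclusion.** This is a cheap improvement of the lowest severity. In cycle 1 the rule acts only on a recorded dosing error that crosses 37.5 U or 75 U. Without one, the received-dose and as-randomised analyses are identical.

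With one such error, type I error stays at 5% if the error is unrelated to prognosis. It rises to about 5.2 to 5.7% at 32 per arm, or about 5.4 to 6.5% at an assumed 16, if the moved patient differs by an assumed 0.5 to 1 SD. These figures rest on an adult SD of 3.46 and a single moved patient, and they illustrate what could happen rather than estimate what did.

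The change is worth making because it takes a post-randomisation event out of the confirmatory comparison using data already held. It does not give a full intention-to-treat analysis: patients randomised but never treated stay excluded under either grouping.

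**What to change.** Before database lock:

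- Run the cycle 1 between-group efficacy comparisons in SAP 5.2 to 5.4 by randomised dose in treated patients.
- Use the same grouping for the related cycle 1 tables so that denominators match: baseline imputation (2.3.1), disposition (3.2), baseline characteristics (4), cycle 1 duration of effect (5.5.1) and cycle 1 subgroup summaries (5.6). The imputation change is for consistency only. Before randomisation the site must "confirm that patient bladder diary records support protocol requirements for urinary urgency incontinence" (Protocol 8.2), so a missing baseline should be rare.
- Keep dose received for safety, for later cycles, and as a cycle 1 efficacy sensitivity analysis.
- Report how many cycle 1 patients change group.
- Record the departure from Protocol 7.1 in SAP 13, which at present lists none.

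If the sponsor prefers to keep the protocol's primary grouping, the minimum is an as-randomised version of the SAP 5.2.1 analysis as a sensitivity analysis, with the same count.

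The randomised assignment is already in IVRS/IWRS, so no new data or patients are needed. The cost is rewording in the SAP sections named, plus 2.1, and the loss of power worked out above if an error occurred.

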**Table 1 BOTOX Treatment Groups Based on Actual Dose Received**

Actual BOTOX Dose Unit Received	BOTOX Treatment Group used for Analysis
< 37.5 U	25 U BOTOX
37.5 U $\geq$ and < 75 U	50 U BOTOX
$\geq$ 75 U	100 U BOTOX

### 2.1.1 Handling Mis-stratification

For any analysis that are by stratum or for analysis that adjusts for stratum effect, the actual strata will be used instead of the strata assigned by the site's entry into the IWRS at randomization.

## 2.2 Visit Windows

The target day and visit window for each post-treatment visit will be referenced to days after treatment. The visit window except for the first three and the last (Week 96) visit windows is defined as:

$[(\text{Target day of current visit} + \text{Target day of previous visit})/2 + 1]$  to  $[(\text{Target day of current visit} + \text{Target day of next visit})/2]$

The visit window for each study treatment cycle is given in the following table. If there are values from multiple visits in a given window, the value collected from the visit closest to the target day will be used to represent the window. If, instead of a single closest visit, 2 visits with values are equidistant from the target day, the value from the first of the 2 visits chronologically will be used to represent the window. For clinical laboratory variables, the last non-missing observation for that visit window will be used. This rule will be applied separately for each variable for non-missing data only. (The exception is because re-runs of laboratory variables may only involve 1 or a few variables and would thus include missing data for many variables).

**Table 2 Analysis Visit Windows**

Visit	Target Day of the Visit a	Study Visit Window a
Screening		≤ Day -1
Treatment 1 Day 1	1	Day 1
Treatment 1 Week 2	15	Day 2 – Day 29
Treatment 1 Week 6	43	Day 30 – Day 64
Treatment 1 Week 12	85	Day 65 – Day 127
Treatment 1 Week 24	169	Day 128 – Day 211
Treatment 1 Week 36	253	Day 212 – Day 295
Treatment 1 Week 48	337	Day 296 – Day 379
Treatment 1 Week 60	421	Day 380 – Day 463
Treatment 1 Week 72	505	Day 464 – Day 547
Treatment 1 Week 84	589	Day 548 – Day 631
Treatment 1 Week 96	673	Day 632 – Day 715/Exit
Treatment X Day 1	1	Day 1
Treatment X Week Y	Repeat same as treatment 1	Repeat same as treatment 1

a Study Day is relative to the most recent treatment day.

## 2.3 Data Conventions

The following data conventions will be applied to all analyses:

- Only data with exceptions will be listed for conciseness. For example, the following would not be listed: normal findings for medical history and physical examination, pregnancy tests results for males or females when not applicable, etc.
- The level of significance used for all statistical tests will be 0.05, 2-sided, unless stated otherwise. P-values ≤0.050 will be considered as statistically significant.
- The type III sums of squares will be used for all analysis of covariance models (ANCOVA) and analysis of variance models (ANOVA).
- The variance for Kaplan-Meier estimates will be calculated using Greenwood's formula.
- Descriptive statistics for continuous variables will include the sample size (n), mean, standard deviation (SD), median, minimum (min), first quartile (Q1), third quartile (Q3), and maximum (max).
- Summary statistics for categorical variables will include the sample size (n), frequency count and percent.

- The Medical Dictionary for Regulatory Activities (MedDRA) dictionary will be used to code all adverse events (AEs) and medical history.
- World Health Organization Drug Dictionary Enhanced (WHO DDE) preferred name and MedDRA will be used to code all medications.
- Study duration from randomization/day 1 will be calculated as:  
$$\text{Study days} = \text{visit date} - \text{randomization/day 1 visit date} + 1.$$
- The Cycle duration for treatment X will be calculated as:  
$$\text{Study days} = \text{visit date} - \text{treatment X date} + 1.$$
- The algorithm presented in [Table 3](#), together with the rules below will be used to impute incomplete or missing dates for adverse events and medications as follows:
  - (a) AE start dates will be imputed as the minimum of the following:
    - initial imputed date, where target date = first study drug injection date.
    - complete end date
  - (b) Medication start dates will be imputed as the minimum of the following:
    - initial imputed date, where target date = first study drug injection date – 1.
    - complete end date
  - (c) AE and Medication end dates will be imputed as the minimum of the following:
    - initial imputed date, where target date = study exit date + 30.
    - Death date
- For each treatment cycle, AEs will be counted with onset date between the day when the study treatment is received and the day before the next treatment is received or exit day.
- Concurrent medication will be classified using the following convention: 1) If the start date of taking medication is after or on the first BOTOX injection date, then it will be counted as concomitant medication; 2) If the start date of taking medication is prior to the first study drug injection date and stop date is on or after first study drug injection date, then it will be counted as both prior medication and concomitant medication.
- All partial dates (including AE, concurrent and prior medication) will be listed “as is” in the data listings.
- All statistical analyses will be performed using SAS® version 9 or higher.

[figure not shown]

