**Table 3 Initial Imputed Date Algorithm**

Available Year (YYYY)	Available Month (MM)			
	Missing	< Target Month	= Target Month	> Target Month
Missing	Target Date	—		
< Target Year	YYYY-12-31	YYYY-MM-LD		
= Target Year	Target Date	YYYY-MM-LD	Target Date	YYYY-MM-01
> Target Year	YYYY-01-01	YYYY-MM-01		

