#### **3.3 Study Duration**

Patients will participate in the study for at least 96 weeks following entry into the study and should have at least 12 weeks follow-up since the last treatment prior to exiting the study. The minimum duration is therefore 96 weeks, and the maximum duration is approximately 108 weeks (for patients who received their last treatment at week 96 with 12 weeks posttreatment follow-up). Thus, patients could receive a maximum of 8 BOTOX treatment cycles. For details on how to analyze duration of exposure to study treatment see Section [6.1.1](#).

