## 6. Safety Analyses

All analyses will be performed on the BOTOX-treated population. Adverse events and all other safety analyses will be presented by BOTOX treatment cycle in this population and grouped according to the actual dose received at that treatment cycle (25, 50, or 100 U of BOTOX as well as an 'All BOTOX' group).

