## **6.2 Adverse Events**

AEs will be coded from the verbatim text into preferred term and the primary SOC by using the MedDRA dictionary. Events will be summarized by BOTOX treatment cycle.

A treatment-emergent adverse event (TEAE) for the study treatment period is an AE with onset after the initiation of study treatment or an AE with onset prior to study treatment that worsened in severity or became serious after the initiation of study treatment.

For a given treatment cycle, a TEAE is an AE with onset after the initiation of cycle treatment or an AE with onset prior to cycle treatment that worsened in severity or became serious after the initiation of cycle treatment.

An AE that stops during treatment cycle 1 and recurs in treatment cycle 2 is considered as a TEAE in treatment cycle 2 if it fulfills the TEAE definition above with respect to initiation of cycle 2 treatment.

The incidence of TEAEs will be summarized and presented for all events and will be tabulated by treatment group as follows:

- i. By relationship to treatment. Classified for all TEAEs and treatment-related TEAEs.
- ii. By descending order of frequency.
- iii. By primary SOC and preferred term. At each level of summarization (overall, primary SOC, and preferred term) a patient will be counted once if he/she reports 1 or more experiences at that level.
- iv. By primary SOC, preferred term and severity. For a given adverse event of a patient, if more than 1 severity grade was reported, the worst severity grade will be included in the tabulation. Statistical hypothesis tests will not be performed for this summary.

All treatment-related TEAEs (study drug-related, and injection procedure-related adverse events) will be presented. In addition, study drug-related and injection procedure-related AEs will be presented separately.

Treatment-related TEAEs will be analyzed by the same procedure outlined above (ii, iii, and iv). In addition, the number and percent of patients discontinued due to treatment-related TEAEs will also be tabulated by treatment group.

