All the summaries discussed above will be based on all AEs observed during the entire treatment cycle. Since the design of this study allows patients to request/receive retreatment from week 12 (day 84) onward, an additional summary showing the number and percentage of patients with TEAEs by preferred term and treatment group in descending order of incidence will be presented for the TEAE observed prior to or on day 84 after each injection cycle. This will allow for a comparison across dose groups for the same duration of time (ie, since patients can request retreatment from week 12 onwards, patients remain in a cycle for varying time periods). Therefore this analysis provides a more direct comparison across dose groups.

In addition, the number and percentage of patients who have a treatment-emergent UTI during the first 2 weeks (14 days), the first 12 weeks (84 days), and during the overall treatment cycle will be presented by the treatment received in each treatment cycle.

A patient listing will be generated for TEAEs, sorted by primary SOC, preferred term, relationship, and severity. In addition, the number and percent of patients discontinued due to TEAEs will also be tabulated by BOTOX treatment group for each BOTOX treatment cycle. A listing will also be generated for patients who discontinued due to TEAEs.

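### Incomplete adverse-event start dates are imputed around the first injection only, so some events from cycle 2 onward are counted in an earlier cycle (minor safety-table issue)

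*SAP*

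**What the plan says.** SAP 2.3(a) sets an incomplete or missing AE start date to the smaller of two dates: the "initial imputed date, where target date = first study drug injection date", and a complete end date. The lookup is in "Table 3 Initial Imputed Date Algorithm". For an event after the first injection it returns:

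- the first injection date, if the year is missing, or if the year is that of the first injection and the month is missing or is the injection month;
- the 1st of the known month, if that month is later than the injection month or in a later year;
- 1 January, if only a later year is known.

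Cycle membership then follows from the date. SAP 2.3: "For each treatment cycle, AEs will be counted with onset date between the day when the study treatment is received"; the interval closes on the eve of the following treatment, or at exit. SAP 6.2: "For a given treatment cycle, a TEAE is an AE with onset after the initiation of cycle treatment" (or an earlier AE that worsened or became serious). SAP 3.3 says that "patients could receive a maximum of 8 BOTOX treatment cycles". SAP 6 presents safety data by cycle, "grouped according to the actual dose received at that treatment cycle". SAP 6.2 adds a table of each "TEAE observed prior to or on day 84 after each injection cycle", and UTI counts over 14 days, 84 days and the whole cycle.

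SAP 2.3, Table 3, 6.2 and 6.3 contain no cycle-specific target date and no tie-break.

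**The concern.** A target at the first injection separates pretreatment from on-treatment events. It cannot separate cycle 2 from cycle 1, or cycle 5 from cycle 4, yet the tables need exactly that. SAP Table 2 counts study days from the most recent treatment, so the visit windows already use the reference that the AE rule lacks.

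The error has one direction. Under SAP 1.1 the dose stays the same or rises at each retreatment, so a misplaced event moves to a cycle with the same or a lower planned dose. The dose group changes only if a retreatment between the imputed and the true onset was an escalation; otherwise only the cycle is wrong. There is one exception: if an incorrect dose was recorded under SAP 2.1, "this dose will represent the actual dose unit received", and that could reverse the dose order.

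At stake are AE counts by cycle and dose, in a study with the safety of repeated treatment among its objectives (Protocol 2.1).

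**Working it through.** The plan gives no figure to reproduce, so this check applies its rule to known onset dates.

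**Example.** First injection 10 March 2015, retreatment 91 days later on 9 June, true onset 14 June, day not recorded. Table 3 gives 1 June. That is 83 days after the first injection, or day 84 when the treatment day is day 1 as in SAP 2.3. An event five days after the second injection is counted in cycle 1, inside its day-84 window.

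**Direction.** The rule was applied to every onset day in cycles 2 and later, for 365 first-injection dates, at 13- and 24-week spacing. No event moved to a later cycle or to pretreatment.

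**Day missing, even onset.** An event is misplaced only if a retreatment fell after the 1st of the month and on or before the true onset.

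- For a retreatment on day j > 1 of a month with m days, the misplaced onset days are j to m, which is m - j + 1 days.
- Summed over j = 2 to m, this is m(m - 1)/2: 465 for 31 days, 435 for 30, 406 for 29 and 378 for 28.
- Over four calendar years (1,461 possible retreatment dates): 28 × 465 + 16 × 435 + 1 × 406 + 3 × 378 = 21,520 misplaced onset days, or 14.73 per retreatment.
- Dividing by cycle length:

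| Cycle length | Misplaced |
|---|---|
| 12 weeks | 21,520 / (1,461 × 84) = 0.175 |
| 16 weeks | 21,520 / (1,461 × 112) = 0.132 |
| 26 weeks | 21,520 / (1,461 × 182) = 0.081 |
| 32 weeks | 21,520 / (1,461 × 224) = 0.066 |

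**Day missing, clustered onset.** With an assumed exponential onset time and 26-week cycles, the misplaced share is 0.231, 0.380 or 0.578 for a mean of 56, 28 or 14 days. For onset within the first 14 days it is about 0.75.

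**Month or whole date missing, even onset.** With only the year known, the share runs from 0.88 (retreatment every 12 weeks) through 0.79 (every 24 weeks) to 0.69 (full 32-week cycles). With the whole date missing it is 1.00, and every such event lands on day 1 of cycle 1.

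**Window tables, cycle 2+, imputed count divided by true count, even onset:**

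| Missing part | 14-day | Day-84 |
|---|---|---|
| Day | about 1.00 | 0.94-1.00 |
| Month | 0.63-0.76 | 0.61-0.72 |
| Whole date | 0 | 0 |

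Day-missing errors largely cancel: about 75% of true 14-day events leave, and an equal number of later events of the cycle are dated back into the window. With clustered onset they do not cancel: both ratios are 0.78, 0.62 or 0.42 for means of 56, 28 or 14 days.

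**The case against.** The strongest objection is materiality. Every percentage is conditional on an incomplete start date, and the documents give no rate. Protocol 9.1.1 has AEs asked about at each visit, and contacts come at weeks 2, 6 and 12 and then every 6 weeks. Staff should seldom be unable to name the month, yet the largest percentages rest on that case. UTI is defined by laboratory results, and urinary retention by residual volume and catheterization (Protocol 9.1.2), so these events will usually carry a date. Exact 12-week cycling, the top of the range, is an edge case. Partial dates stay visible in the listings (SAP 2.3), recruitment was stopped (SAP 15), and retreatment doses are chosen by the investigator, so comparisons between doses in later cycles are not randomised. All of this stands and keeps the point minor. It does not remove the mismatch: listings do not correct the tables.

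A second objection is that re-anchoring can do harm. With even onset it turns the day-missing 14-day ratio from about 1.00 into 2.05, and the day-84 ratio from 0.94-1.00 into 1.00-1.18, because same-month events are placed on the treatment day. This also stands, so the fix below is limited to cycle and dose-group assignment.

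A reader might go further and infer that the rule hides a dose-related safety signal, or empties the early windows of later cycles. The documents do not support that. Most day-missing events stay in the right cycle under even onset, and a material net loss from the windows needs month-missing or fully missing dates, or clustered onset. Nor is every incomplete date moved to the first injection; Table 3 does that only in the cases listed above.

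**Conclusion.** The point holds as a minor safety-table issue. The stated rule puts some events from cycle 2 onward into an earlier cycle, with the same or a lower planned dose, and nothing else in the SAP corrects it. With even onset and 12- to 32-week intervals, the misplaced share is about 7-18% (day missing), 69-88% (month missing) and 100% (whole date missing). With onset clustered after injection, the day-missing share is 23-58%. Interval, onset pattern and 26-week cycle length are assumptions.

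The number of AEs affected cannot be derived from the documents and is probably small. Cycle 1 tables can gain events that belong to later cycles, but by how many is equally unknown, so no claim of a biased randomised comparison follows. No efficacy analysis is touched.

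**What to change.** In SAP 2.3(a), for assigning cycle and dose group only, set the AE target date to the most recent study treatment before the visit at which the AE was first reported, or to the first injection if there is none. Keep the known date parts and the minimum with a complete end date. In the example above, the 14 June event would be dated 9 June and stay in cycle 2.

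Do not let the re-anchored date alone decide membership of the 14-day or day-84 windows. Footnote the number of AEs whose membership depends on an imputed date, and show the day-84 table with and without them. With even onset, day-missing day-84 counts are then 1.00-1.18 and 0.82-1.00 times the true count, so the pair brackets it.

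Report how many AEs have imputed start dates, and how many change cycle or dose group compared with the first-injection rule. Those counts will show whether the issue matters.

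The documents do not say whether the AE eCRF stores the reporting visit. If it does not, keep the current rule and report the reassignment count as a sensitivity analysis, using the latest treatment compatible with the known date parts. That assignment errs towards later cycles (6-15% of day-missing and 58-76% of month-missing cycle 2+ events), so it should not drive the main tables.

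The cost is a few lines of SAP text, a small programming change and one paired table. Some AEs reported late, after a retreatment, may be credited to the later cycle. In a simulation with an assumed 20% reported one visit late, this affected 1-3% of day-missing and 2-8% of month-missing cycle 2+ events.
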